## 10.6.3 Analysis Methods

- 1) The analysis results will be summarized by squamous NSCLC and non-squamous NSCLC separately and totality.
- 2) For 12-lead ECG parameters (observed values of RR interval, QT interval, Fridericia's corrected QT interval [QTcF], QRS width, and PR interval, and their changes from baseline [ $\Delta$ QTcF,  $\Delta$ QRS, and  $\Delta$ PR]), observed value (HR) and change from baseline ( $\Delta$ HR) of heart rate, summary statistics and frequency distribution for each category will be summarized at each time point.
- 3) For maximum QTcF, maximum  $\Delta$ QTcF, maximum QRS, maximum PR, and maximum heart rate of subjects, frequency distribution for each category will be calculated.

Item	Classification
RR (ms) (observed value)	$\leq 600$ , $> 600\text{--}1200$ , $> 1200$
PR (ms) (observed value)	$\leq 120$ , $> 120\text{--}200$ , $> 200$
QRS (ms) (observed value)	$\leq 60$ , $> 60\text{--}109$ , $> 109$
Heart rate (observed value)	$\leq 50$ , $> 50\text{--}100$ , $> 100$
QT interval, QTcF (ms) (observed value)	$\leq 450$ , $> 450\text{--}480$ $> 480\text{--}500$ , $> 500$
$\Delta$ QTcF (ms) (change from baseline)	$\leq 30$ , $> 30\text{--}60$ , $> 60$

## 11 Anti-drug Antibody Analysis

### 11.1 Analysis Set

Analysis will be performed in the Anti-drug Antibody Analysis Set.

### 11.2 Analysis Items and Data Handling

#### 1) Analysis Items

Presence of the anti-ONO-4538 antibody

#### 2) Data Handling

##### (1) Handling per sample

Samples will be handled as follows.

###### [1] Baseline positive samples

Samples testing positive for anti-ONO-4538 antibodies at baseline. Subjects with at least one baseline neutralizing positive sample for anti-ONO-4538 antibodies including baseline positive ones.

###### [2] Anti-ONO-4538 antibody-positive samples

Samples were obtained within 100 days of final dose meeting either of the following criteria:

1. Samples after the first dose of the investigational product (collected from subjects who tested negative for anti-ONO-4538 antibodies at baseline) testing positive for anti-ONO-4538 antibodies.
2. Samples after the first dose of the investigational product (collected from subjects who tested positive for anti-ONO-4538 antibodies at baseline) testing positive for anti-ONO-4538 antibodies and with titers at least 4-fold higher than those at baseline.

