**Table 3-2 Study schedule (Cycles 2 and beyond)**

Category	Treatment phase (Cycles 2 and beyond)			
	1 	15		43 
		Before administration	After administration	
Allowable range (days)	1	-3 to +7		-6 to +7
Visit	V n-1	V n-2		V n-3
Investigational product administration 	○	○		○
Performance Status	○ 			
Vital signs/weight/percutaneous oxygen saturation	○ 	○ 		○ 
Chest X-ray 				
12-lead ECG	○ 			
Hematology tests, blood biochemistry tests, urinalysis	○ 			
Immunology/hormone tests				
Serum drug concentration 	○ 	○ 	○ 	
Anti-ONO-4538 antibody 	○ 	○ 		
Tumor markers 		○		
Diagnostic imaging (e.g., CT, MRI)				○
Concomitant drugs/adverse events	←	→		

1. Administer the investigational product after at least 10 days have passed since the most recent dose.
2. Also perform at unscheduled times as necessary if, during the study (from the time of informed consent to the completion of the final tests (other than the determination of outcome) specified in the protocol), signs, subjective and objective symptoms, or test findings suggest respiratory disease.
3. To be collected until the end of the 1-year period after the start of investigational drug administration (i.e., Cycle 9).
4. Analyze tumor markers whenever possible in each subject with a tumor marker at a level exceeding the normal range. Perform tumor marker analysis when required.
5. For subjects again proceeding to the treatment phase, administer the investigational product on Day 1 of the next cycle within the Day 43 allowable range (i.e., Days 37 to 50). Proceed to the follow-up phase ([Table 3-3](#)) on completing the treatment phase.
6. Unless medically necessary, vital signs will be measured no sooner than 2 days, and other tests will be performed no sooner than 8 days after the previous measurement.
7. Perform before administering the investigational product.
8. Other than weight.
9. Perform only in Cycle 4.
10. Perform only in Cycles 2, 4, 5, 7, and 9.
11. Perform only in Cycle 3.
12. Collect sample immediately before the completion of investigational product administration.

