###### [3] Anti-ONO-4538 antibody-negative sample

Samples after the first dose of the investigational product testing negative for anti-ONO-4538 antibodies (excluding missing ones), including baseline negative samples (excluding missing ones).

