##### (2) Handling per subject

###### [1] Baseline positive subjects

Subjects with baseline positive samples as defined in (1) but subjects without any positive samples for anti-ONO-4538 antibodies after the first dose of the investigational product. And “baseline neutralizing positive” subjects with at least one positive sample for anti-ONO-4538 antibodies after the first dose of the investigational product including neutralizing ones within “baseline positive” subject.

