###### [2] Anti-ONO-4538 antibody-positive subjects

Subjects with at least one positive sample for anti-ONO-4538 antibodies after the first dose of the investigational product. They will be classified as follows.

1. Persistent positive: Subjects with two or more samples collected at consecutive time points after the first dose of the investigational product and testing positive for anti-ONO-4538 antibodies with a minimum interval of 16 weeks (there is a time window for one week) between the first and last positive samples.
2. Only the last sample positive: Subjects for whom only the last sample is positive for anti-ONO-4538 antibodies.
3. Other positive: Other subjects (not meeting 1 or 2) with samples positive for anti-ONO-4538 antibodies.
4. Neutralizing positive: Subjects with at least one positive sample for anti-ONO-4538 antibodies including neutralizing ones.

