### [3] Anti-ONO-4538 antibody-negative subjects

Subjects without any positive sample for anti-ONO-4538 antibodies after the first dose of the investigational product.

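### The 100-day limit on antibody-positive samples is worded so that on-treatment positives more than 100 days before the final dose do not count

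*SAP*

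**What the plan says.** **Sample level.** SAP 11.2 2)(1)[2] sets a lead-in condition, "Samples were obtained within 100 days of final dose meeting either of the following criteria", and then two criteria. The first, for baseline-negative subjects, is "Samples after the first dose of the investigational product (collected from subjects who tested negative for anti-ONO-4538 antibodies at baseline) testing positive for anti-ONO-4538 antibodies". The second, for baseline-positive subjects, also requires a titer at least 4-fold above baseline. A negative sample, under (1)[3], must actually test negative.

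**Subject level.** SAP 11.2 2)(2) builds the subject classes from these samples.
- Positive: "Subjects with at least one positive sample for anti-ONO-4538 antibodies after the first dose of the investigational product".
- Negative: "Subjects without any positive sample for anti-ONO-4538 antibodies after the first dose of the investigational product".
- Baseline positive: "Subjects with baseline positive samples as defined in (1) but subjects without any positive samples for anti-ONO-4538 antibodies after the first dose".
- Persistent positive: consecutive positives "with a minimum interval of 16 weeks (there is a time window for one week) between the first and last positive samples".

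**Sampling and treatment.** SAP Tables 3-1 and 3-2 schedule antibody samples in Cycle 1 and at selected later visits, ending with Cycle 9 at one year. Table 3-3 footnote 2 plans follow-up samples only for subjects who enter follow-up within that year, with one, where possible, 6 to 12 weeks after the last dose. Treatment itself runs until PD (SAP 3.4).

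**Use.** The classes give the proportions in SAP 11.3. They are also a subgroup factor in 12.4, applied to the centrally assessed response rate (9.2.5) and to select adverse events (10.1.4).

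**The concern.** The 100-day window is tied to the final dose and does not say before or after. The phrase about the first dose inside the two criteria is an additional condition; it does not replace the window. A sample taken 150 days before the final dose is after the first dose, but it is not within 100 days of the final one, so it fails the definition even if the assay is positive. It is not a negative sample either, because it did not test negative, so it has no class.

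If the rule is programmed as written, the number of lost samples grows with time on treatment, and time on treatment runs to progression. A subject with only early positives would stay in the Anti-drug Antibody Analysis Set (SAP 4.1 needs only a baseline and one later determination) but move out of the positive class. The positive and persistent-positive proportions could then only fall. In the 12.4 subgroups, the subjects moved would tend to be those treated longest.

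**Working it through.** There is no stated figure to reproduce, because the point concerns a classification rule. The check applies the wording to the sampling calendar.

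**Inputs.** Cycle length 42 days and a dose every 14 days (SAP 3.4). Antibody samples after the first dose: Cycle 1 Days 15 and 29 (Table 3-1); Day 1 of Cycles 2, 4, 5, 7 and 9, and Day 15 of Cycle 3 (Table 3-2 footnotes 10 and 11). Follow-up samples: at 28 days and, if possible, at 6 to 12 weeks after the final dose (42 to 84 days), only if follow-up starts within one year (Table 3-3). No dose delays are assumed.

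**Sample days.** Study day = (cycle − 1) × 42 + day in cycle. For example, Cycle 3 Day 15 = 2 × 42 + 15 = 99, and Cycle 9 Day 1 = 8 × 42 + 1 = 337. The eight samples fall on Days 15, 29, 43, 99, 127, 169, 253 and 337.

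**Literal rule.** With final dose on Day L, a sample on Day s counts only if |s − L| ≤ 100. An on-treatment sample is therefore lost once L ≥ s + 101.

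| Final dose (Day) | On-treatment samples taken | Inside window | Lost | Planned follow-up samples | Eligible in total |
|---|---|---|---|---|---|
| 127 | 5 | 29, 43, 99, 127 | 1 of 5 | up to 2 | up to 6 |
| 155 | 5 | 99, 127 | 3 of 5 | up to 2 | up to 4 |
| 281 | 7 | 253 | 6 of 7 | up to 2 | up to 3 |
| 337 | 8 | 253, 337 | 6 of 8 | up to 2 | up to 4 |
| 407 | 8 | 337 | 7 of 8 | none | 1 |
| 449 | 8 | none | 8 of 8 | none | 0 |

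The last sample drops out when L exceeds 337 + 100 = 437; the first nominal dose day after that is Day 449. From there no scheduled sample can make a subject positive. Treatment that long is foreseen: Protocol Table 4-2 footnote 13 sets an imaging interval for Cycle 30 onward, and Cycle 30 Day 1 is 29 × 42 + 1 = Day 1219.

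**Persistent positive.** The required gap is 16 × 7 = 112 days, or 112 − 7 = 105 with the one-week window. Any two on-treatment samples inside the literal window lie between L − 100 and L, so they are at most 100 days apart. On the nominal calendar the largest span is 127 − 29 = 98 days, at L = 127. Since 98 < 105, the class cannot be met without a post-treatment sample.

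**Intended rule.** With the window read as after the first dose and up to L + 100, all eight on-treatment samples qualify for any L at which they were taken. So do the follow-up samples at L + 28 and at L + 42 to L + 84.

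**The case against.** The strongest reply is that nobody would program the literal rule. The criteria supply the start (after the first dose) and the lead-in supplies the end. The SAP uses the same end-only shorthand elsewhere: the opening of Section 10 describes the safety period only by the 28 days after the final dose, and 10.1.2 shows that it starts at the first dose. The persistent-positive class and the 6-to-12-week follow-up sample both fit an upper limit after the last dose. The subject-level definitions do not repeat the 100 days. The primary response rate is untouched, and the affected tables are descriptive, since SAP 12.2 says no tests will be performed.

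Most of this stands, and it makes the intent clear. It does not remove the defect. The 28-day period is written out in full in 10.1.2, but the 100-day window is written out nowhere. The subject-level text relies on positive samples, which the sample-level text defines with the limit included. A validator following the text would apply a rule that the SAP's own persistent-positive class does not fit.

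A reader might go further and infer that long-treated subjects with early positives are simply classed as negative, or that the reported proportions will be too low. The documents do not support either. Even literally, the class changes only if no other positive falls inside the window, and subjects entering follow-up within a year have up to two further eligible samples. A baseline-positive subject whose only qualifying rise is early meets the *baseline positive* definition, while also fitting the wording for negative. Whether any proportion is too low depends on how the rule is programmed, which the documents do not show.

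**Conclusion.** The point holds as a wording defect with a real consequence if the text is followed. On-treatment positives more than 100 days before the final dose do not count, and a subject with no other in-window positive loses the antibody-positive class. At sample level the loss is 3 of 5 on-treatment samples for a final dose on Day 155, 6 of 7 for Day 281, and all 8 after Day 437; only in the last case is there no planned follow-up sample to compensate. Persistent positivity cannot be shown from on-treatment samples alone.

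The effect is confined to the descriptive proportions in SAP 11.3 and the antibody subgroup tables under 12.4. Its size at subject level cannot be stated, because the documents give neither the antibody incidence nor the number of subjects treated beyond these days. The day counts assume nominal visits; delays and visit windows move the cut-offs but not the conclusion. That the sponsor means an upper limit after the last dose is inferred from the surrounding definitions and is not written in the SAP.

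**What to change.** Replace the lead-in of SAP 11.2 2)(1)[2] with: *Samples obtained after the first dose and no later than 100 days after the final dose that satisfy one of the two criteria below.* All planned on-treatment and follow-up samples then qualify whatever the treatment duration.

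The cost is one phrase in the SAP, with no new data. If the antibody datasets have already been programmed, check which window was used and state it with the results.

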###### [3] Anti-ONO-4538 antibody-negative sample

Samples after the first dose of the investigational product testing negative for anti-ONO-4538 antibodies (excluding missing ones), including baseline negative samples (excluding missing ones).

##### (2) Handling per subject

###### [1] Baseline positive subjects

Subjects with baseline positive samples as defined in (1) but subjects without any positive samples for anti-ONO-4538 antibodies after the first dose of the investigational product. And “baseline neutralizing positive” subjects with at least one positive sample for anti-ONO-4538 antibodies after the first dose of the investigational product including neutralizing ones within “baseline positive” subject.

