### **11.3 Analysis Methods**

The following will be calculated: the proportions of baseline positive subjects, anti-ONO-4538 antibody-positive subjects and anti-ONO-4538 antibody-negative subjects in the Anti-drug Antibody Analysis Set; the proportions of "persistent positive" subjects, "only the last sample positive" subjects and "other positive" subjects among anti-ONO-4538 antibody-positive subjects; and if necessary, the proportion of "baseline neutralizing positive" subjects and "neutralizing positive" subjects among anti-ONO-4538 antibody-positive subjects. The analysis results will be summarized by squamous NSCLC and non-squamous NSCLC separately and totality.

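### SAP 11.2 and 11.3 define *baseline neutralizing positive* inconsistently, and on the literal text its proportion is zero whatever the baseline assay shows

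*SAP*

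**What the plan says.** Four parts of the SAP bear on this category.

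- **11.2 2)(1)[1], samples.** After defining a baseline positive sample, the text adds: "Subjects with at least one baseline neutralizing positive sample for anti-ONO-4538 antibodies including baseline positive ones". It contains no post-dose condition. The revision history records this sentence as added in version 2.0 to clarify the definition.
- **11.2 2)(2)[1], subjects.** *Baseline positive* subjects are "Subjects with baseline positive samples as defined in (1) but subjects without any positive samples for anti-ONO-4538 antibodies after the first dose". The next sentence describes *baseline neutralizing positive* as "subjects with at least one positive sample for anti-ONO-4538 antibodies after the first dose of the investigational product including neutralizing ones within" the *baseline positive* group.
- **11.2 2)(2)[2], subjects.** Antibody-positive subjects are "Subjects with at least one positive sample for anti-ONO-4538 antibodies after the first dose of the investigational product. They will be classified as follows". Item 4 of that list is a separate *neutralizing positive* category. For a subject positive at baseline, a post-dose sample counts as positive only if it was taken within 100 days of the final dose and is "testing positive for anti-ONO-4538 antibodies and with titers at least 4-fold higher than those at baseline" (11.2 2)(1)[2]).
- **11.3.** The proportions of *baseline neutralizing positive* and *neutralizing positive* are taken as "subjects among anti-ONO-4538 antibody-positive subjects", and only if necessary.

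**The concern.** The second sentence of 11.2 2)(2)[1] requires of a subset what the first sentence rules out for its parent group. The denominator in 11.3 repeats the problem, because antibody-positive subjects are those with a post-dose positive sample and *baseline positive* subjects are those without one.

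If the line is programmed as written, the table shows no baseline neutralizing antibodies for a purely definitional reason, and a reader could take that as an assay finding. A programmer who works from the sample-level sentence, or who reads *baseline positive* loosely, would print a different number under the same label.

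**Working it through.** The plan states no figure for this category, so there is nothing to reproduce. The check is one of logic.

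**Definitions as sets.** Let B be a positive baseline sample, N a neutralizing baseline sample, and P at least one qualifying positive sample after the first dose.

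- *Baseline positive* subject (11.2 2)(2)[1], first sentence): B and not P.
- *Baseline neutralizing positive* (second sentence): within (B and not P), and P, with a neutralizing result. This contains P and not-P, so it is empty.
- Antibody-positive subject (11.2 2)(2)[2]): P. Its overlap with (B and not P) is empty.
- Sample-level wording (11.2 2)(1)[1]): B and N, with nothing required after the first dose.

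**Enumeration.** Each post-dose sample is coded for: tests positive, titer at least 4-fold above baseline, within 100 days, neutralizing. A sample that tests negative cannot have a 4-fold rise or be neutralizing, which leaves 10 codings. With 1 to 3 post-dose samples there are 10 + 100 + 1,000 = 1,110 patterns. With three baseline states (negative, positive, positive and neutralizing) there are 3 × 1,110 = 3,330 profiles. These are logical possibilities, not expected rates.

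| Reading | Profiles in category | Of these, antibody-positive |
|---|---|---|
| Literal, *positive sample* meaning the same in both sentences | 0 | 0 |
| Literal, but first sentence uses the 4-fold rule and second uses any positive assay result | 858 | 0 |
| Sample-level wording: neutralizing at baseline | 1,110 | 526 |
| *Baseline positive* read as any subject with a positive baseline sample, plus a qualifying neutralizing post-dose sample | 582 | 582 |

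For the last row, 1 of the 10 codings is both qualifying and neutralizing in a baseline-positive subject. Each of the two baseline-positive states therefore gives (10 − 9) + (100 − 81) + (1,000 − 729) = 291 profiles, and 2 × 291 = 582. The count is the same 291 whether or not the baseline sample was neutralizing, so this reading does not measure neutralization at baseline.

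**Illustration with three invented subjects, taken as the whole analysis set.**

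| Subject | Baseline | After first dose | Antibody-positive | Literal | Sample-level wording | Loose reading |
|---|---|---|---|---|---|---|
| A | positive, neutralizing | no qualifying positive | no | no | yes | no |
| B | positive, neutralizing | 4-fold rise, not neutralizing | yes | no | yes | no |
| C | positive, not neutralizing | 4-fold rise, neutralizing | yes | no | no | yes |

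The 11.3 denominator is B and C. The literal text gives 0/2. The sample-level wording gives 1/2 (B) and loses A. The loose reading also gives 1/2, but the subject counted is C, who was not neutralizing at baseline. The baseline proportion over all three is 2/3 (A and B).

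**The case against.** A reader might infer that no subject can ever qualify and that the reported proportion must always be zero. The documents do not support that, for three reasons.

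- The sample-level sentence is part of the current SAP and gives a definition that subjects can meet. Some who meet it fall inside the 11.3 denominator.
- *Baseline positive* in the second sentence could be meant at sample level, as any subject whose baseline sample was positive. The category then has members, all of them antibody-positive, and the 11.3 denominator fits. The SAP puts the term in quotation marks directly after defining it, which favors the literal reading but does not make it the only one.
- The proportion is produced only if necessary, and with no antibody-positive subjects it would be 0/0.

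These points stand and limit the claim. They do not remove the defect. The loose reading sets aside the sentence just before it and counts post-dose neutralization under a baseline label. The sample-level wording, combined with the 11.3 denominator, still drops every subject who was neutralizing at baseline and had no qualifying post-dose positive sample.

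It is also fair to say that the practical size is unknown. The documents give neither the number of baseline-positive subjects nor the share who were neutralizing.

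**Conclusion.** The point holds as a conflict among 11.2 2)(1)[1], 11.2 2)(2)[1] and 11.3. On the literal subject-level text the proportion is 0 or 0/0, whether the true share neutralizing among baseline-positive subjects is 0% or 100%. On other readings it can be non-zero, and those readings count different subjects.

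The matter is minor. It touches one conditional descriptive line. The proportions of baseline positive, antibody-positive and antibody-negative subjects, the split into persistent, last-sample-only and other positive, and the antibody subgroup in 12.4 do not use this category. Neither does any efficacy result or the sample size. The conclusion rests only on the SAP wording and on no assumption about prevalence.

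**What to change.** 1. Define *baseline neutralizing positive* once, at subject level, as a subject whose baseline sample is positive and neutralizing. This agrees with 11.2 2)(1)[1].
2. Delete the post-dose condition from the second sentence of 11.2 2)(2)[1], and state that the category is drawn from all subjects with a positive baseline sample, whatever their post-dose results.
3. In 11.3, report the proportion with the ADAS as denominator. SAP 4.1 4) requires a baseline antibody determination for every ADAS member, so the denominator is always available. A second proportion among all subjects with a positive baseline sample is optional.
4. Keep *neutralizing positive* (11.2 2)(2)[2], item 4) as the post-dose category among antibody-positive subjects.

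The cost is a few sentences of SAP text. No new data are needed if positive baseline samples were tested for neutralization. The sample-level wording presupposes such results, but the documents do not state which samples receive that test. The table should therefore show how many positive baseline samples have no neutralizing result.
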